# **10.2.** Clinical Status by Karnofsky Performance

Clinical deterioration is defined as a decline in the Karnofsky performance status (Appendix 1) from 100% or 90% to  $\leq$  70%; a decline of  $\geq$  20% from 80% or less; or a decline from any baseline value to 50% or less, for at least 7 days, unless attributable to comorbid events (e.g., seizures, medication adverse effects, complications of therapy, cerebrovascular events, infection, etc.). Clinical status must be recorded as Improved, Stable, or Worsened.

# 10.3. Corticosteroid Dose

At the time of each disease assessment, the corticosteroid intake will be compared with corticosteroid intake at the time of the last disease assessment. The changes will be recorded as Increased, Unchanged, or Decreased. Increases or decreases in corticosteroid dose should be clinically justified.

Note: Increases in corticosteroid dose for reasons other than disease control do not need to be taken into consideration when making this comparison.

# **10.4.** Overall Disease Assessment

Based on radiological assessments, clinical status, and corticosteroid use, an overall evaluation of CR, PR, SD, or PD should be made at each disease assessment after baseline according to the RANO criteria (Appendix 2).

# 11. SAFETY

# **11.1.** Safety Parameters

The NCI-CTCAE; Version 4.03 will be used for grading toxicities unless otherwise specified. Patients will be monitored throughout the treatment and follow-up period for occurrence of AEs (acute, delayed, and/or cumulative), as well as for changes in clinical status, vital sign measurements, and laboratory data. Safety parameters to be measured/assessed include vital sign measurements, physical examinations, concomitant medications, hematology, serum chemistries, urinalysis, pregnancy testing, ECGs, and Karnofsky performance status.

# **11.2.** Adverse Event Definition

An adverse event (AE) is defined as any untoward medical occurrence associated with the use of a drug in humans, whether or not considered drug related. AEs include:

- Suspected adverse drug reactions (abbreviated as either SADR or SAR). This may be serious or not serious.
- Reactions from drug overdose, abuse, withdrawal, sensitivity, or toxicity.
- Significant changes or abnormalities, when compared to baseline, in structure (sign), function (symptom), clinical laboratory results, ECG results, or physiological testing. This includes any worsening of a pre-existing condition temporally associated with the use of study drug.
- Other medical events, regardless of their relationship to the study drug, such as injury, surgery, accidents, extensions of symptoms, or apparently unrelated illnesses.

Findings existing prior to signing informed consent will be recorded as medical history. For the purpose of data collection, all untoward events that occur after informed consent through 30 days after last dose of study treatment are to be recorded on eCRFs by the investigational site. This requirement includes AEs from unscheduled as well as scheduled visits.

### An AE does not include:

- Medical or surgical procedures (e.g., surgery, endoscopy, tooth extraction, transfusion); when the condition that leads to the procedure is an AE.
- Pre-existing diseases, or conditions or laboratory abnormalities present or detected prior to the screening visit, those do not worsen.
- Situations where an untoward medical occurrence has not occurred (e.g., hospitalization for elective surgery, social, and/or convenience admissions).
- Overdose of either tesevatinib or a concomitant medication without any signs or symptoms, unless the patient is hospitalized for observation.

# **11.3.** Evaluating Adverse Events

The investigator will determine the seriousness, intensity, and causality of an AE associated with the use of the study drug (i.e., events where there is a reasonable possibility that the event may have been caused by the study drug) based on the definitions that follow.

# 11.3.1. Serious Adverse Events

### (Notify sponsor or designee within 24 hours of first awareness)

The SAE definition and reporting requirements are in accordance with the ICH Guideline for Clinical Safety Data Management, Definitions, and Standards for Expedited Reporting, Topic E2A, with Title 21 Part CFR 312.32, and the Guidance for Industry and Investigators Safety Reporting Requirements for INDs and BA/BE Studies.

SAE: An adverse event is considered "serious" if, in the view of either the investigator or sponsor, it results in any of the following outcomes:

- **Death:** This includes any death that occurs while the patient is "on study" as well as any death that occurs within 30 days after last dose of study drug administration.
  - *Note*: Death is an outcome of an AE, and not an AE in itself. The event(s) that caused death (e.g., illness, accident) is the SAE. Death due to any other cause(s) must also be reported as an outcome of the reportable SAE.
- Life-threatening adverse event: An AE or suspected adverse reaction is considered "life-threatening" if, in the view of either the investigator or sponsor, its occurrence places the patient or patient at immediate risk of death. It does not include an AE or suspected adverse reaction that, had it occurred in a more severe form, might have caused death).
- **Inpatient hospitalization or prolongation of existing hospitalization:** In the absence of an AE, the investigator should not report hospitalization or prolongation of hospitalization. This is the case in the following situations:
  - Hospitalization or prolongation of hospitalization is needed for a procedure required by the protocol
  - Hospitalization or prolongation of hospitalization is part of routine procedure followed by study center
  - Hospitalization for survey visits or annual physicals

In addition, a hospitalization planned before the start of the study for a pre-existing condition which has not worsened does not count as an SAE.

- Persistent or significant incapacity or substantial disruption of the ability to conduct normal life functions
- Congenital anomaly/birth defect

 Important medical event: An event that may not result in death, be life threatening, or require hospitalization may be considered serious when, based upon appropriate medical judgment, it may jeopardize the patient and may require medical or surgical intervention to prevent one of the outcomes listed in this definition.

Some serious events will not be reported as SAEs, including:

- Disease progression
- Death due to disease progression occurring more than 30 days after the last dose of study drugs
- Medical or surgical procedures when the condition that leads to the procedure is an AE
- Pre-existing diseases, or conditions or laboratory abnormalities present or detected prior to the screening visit, that do not worsen
- Situations for which an untoward medical occurrence has not occurred (e.g., hospitalization for elective surgery, social and/or convenience admissions)

### 11.3.2. Suspected Unexpected Serious Adverse Reactions (SUSAR)

#### (Notify sponsor or designee within 24 hours of first awareness)

A suspected unexpected serious adverse reaction is any adverse drug event, the specificity or severity of which is not consistent with those noted in the current protocol and/or Investigator's Brochure (IB). This refers to any AE that has not been previously observed (e.g., included in the IB), rather than from the perspective of such an event not being anticipated from the pharmacological properties of the product.

### 11.3.3. Unexpected Adverse Events

An AE is considered "unexpected" if it is not listed in the Investigator Brochure (IB) or is not listed at the specificity or severity that has been observed; or, if an IB is not required or available, is not consistent with the risk information described in the General Investigational Plan or elsewhere in the current application. Also refers to AEs that are mentioned in the IB as occurring with a class of drugs or as anticipated from the pharmacological properties of the drug, but are not specifically mentioned as occurring with the particular drug under investigation.

### 11.3.4. Non-Serious Adverse Events

All other AEs, not fulfilling the previous definitions, are classified as non-serious.

### 11.3.5. Protocol-Related Adverse Events

AEs that are not test drug related may nevertheless be considered by the investigator or the Medical Monitor to be related to the conduct of the clinical study. That is, the event may be related to the fact that a patient is participating in the study. For example, a protocol-related AE

may be an event that occurs during a washout period or that is related to a procedure required by the protocol.

### 11.3.6. Relationships/Causality to Study Drug

The investigator will attempt to assess the relationship of the event to study drug using a 5- point scale (not related, unlikely-related, possibly related, probably related, or definitely related).

### 11.3.7. Recording Adverse Events

All AEs (including SAEs) are to be accurately recorded on the Adverse Event page of the patient's eCRF. The date of onset as well as the duration of the event also should be recorded. In addition, the method used to treat the AE and the outcome of the AE also will be noted. The investigator will assess the relationship of the event to study drug (not related, unlikely-related, possibly related, probably related, or definitely related).

### 11.3.8. Adverse Event Monitoring and Follow-up

The investigator will follow all patients who experience adverse events until there is a return to the patient's baseline condition, Grade 1 severity or until a clinically satisfactory resolution has been achieved. The appropriate follow-up visits must be scheduled and the specific tests repeated or performed as necessary. Where a diagnosis is possible, it is preferable to report this diagnosis rather than a series of terms (signs/symptoms) relating to the diagnosis.

### **11.3.9.** Laboratory and ECG Abnormalities

For the purposes of grading creatinine, the upper limit of normal – not the patient's baseline value - will be used to determine grade.

For the purpose of grading sodium, values of 126–130 mmol/L will be considered to be Grade 2 and values of 120–125 mmol/L will be considered Grade 3.

For the purposes of this study, ECG abnormalities will be handled in the same manner as laboratory abnormalities.

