Patients who develop $\geq$ Grade 3 adverse event considered by the investigator to be related to study drug (with the exception of asymptomatic Grade 3 elevations of amylase or lipase, Grade 3 elevation of glucose in a patient receiving systemic corticosteroids, Grade 3 creatine phosphokinase [CPK] elevation in the absence of muscle symptoms, or Grade 3 sodium values $\geq$ 126 mmol/L in a patient with diarrhea) will have study treatment interrupted until the $\geq$ Grade 3 drug-related toxicities have resolved to $\leq$ Grade 1 (refer to Section 9.1.3).
Once toxicities have resolved to $\leq$ Grade 1, the patient may resume study treatment at a reduced dose of 250 mg/day. No more than one dose reduction is permitted. Patients who require more than one dose reduction will have study drug discontinued and enter the Follow-up Period.
Patients for whom toxicity persists beyond 21 days despite dose interruption may resume study treatment only with permission from the responsible Medical Monitor.
If study treatment is withheld, the patient should be instructed not to make up the withheld doses.
Study treatment will continue until disease progression, unacceptable toxicity, patient or physician decision to discontinue, or death. Assessments for disease response will occur at week 4 and 8 and then every 8 weeks using the RANO criteria (see Appendix 2).
Upon treatment discontinuation, patients will be followed every 8 weeks for survival.
Tumor samples will be used for exploratory biomarker research including, but not limited to, evaluation of EGFRvIII expression by immunohistochemistry (IHC) or real-time Polymerase Chain Reaction (PCR). An appropriate histopathological definition and cutoff for EGFRvIII pos tumors will be established, and outcome in this subpopulation will be evaluated in addition to the overall study population.
To characterize the safety and tolerability profile of tesevatinib, patients will be monitored throughout the study for adverse events (all grades), serious adverse events, and any adverse events requiring drug interruption or discontinuation. Patients will undergo safety evaluations, including physical examination (PE), vital sign measurements, hematology, serum chemistry, urinalysis and electrocardiogram (ECG).

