### 9.1.3. Dose Modifications and Delays for Toxicity Related to Study Drug

Patients who develop  $\geq$  Grade 3 adverse event(s) considered by the investigator to be related to study drug (with the exceptions noted below) will have study treatment interrupted until all drug-related toxicities have resolved to  $\leq$  Grade 1. Once these toxicities have resolved to  $\leq$  Grade 1, the patient may resume study treatment at a reduced dose of 250 mg/day. No more than one dose reduction is permitted. Patients who require more than one dose reduction will have study drug discontinued and enter the Follow-up Period.

The exceptions are:

- asymptomatic Grade 3 elevations of amylase or lipase,
- Grade 3 elevation of alkaline phosphatase in a patient known to have bone metastases,
- Grade 3 elevation of glucose in a patient receiving systemic corticosteroids,
- Grade 3 creatine phosphokinase [CPK] elevation in the absence of muscle symptoms,
- Grade 3 sodium values  $\geq 126 \text{ mmol/L}$  in a patient with diarrhea)

Patients for whom toxicity persists beyond 21 days despite dose interruption may resume study treatment at a reduced dose of 250 mg/day only with permission from the responsible Medical Monitor.

If study treatment is withheld, the patient should be instructed not to make up the withheld doses.

T٤	ıb	le	5	:

ed AEs

Occurrence	Grade 1	Grade 2	Grade 3	Grade 4

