First appearance	
 
No action with study drug
 
For diarrhea start loperamide, monitor for dehydration
 
For rash start topical steroids (see Section 9.1.4.2)
 
For QTc prolongation no action
 
	
 
No action with study drug
 
For diarrhea start/increase loperamide, monitor for dehydration
 
For rash topical steroids ± doxycycline (see Section 9.1.4.2)
 
For QTc check con-meds and electrolytes, correct as indicated
 
For confirmed pneumonitis interrupt and consult Medical Monitor
 
	
 
Interrupt treatment until resolved to Grade 0-1. If interruption < 21 days restart at 250 mg/day. If interruption ≥ 21 days, check with Medical Monitor.
 
In addition, for QTc check con- meds, electrolytes and consult Medical Monitor (see Section 9.1.4.3.1 for restarting and monitoring instructions).
 
For creatinine in absence of renal dysfunction no interruption.
 
	Discontinue. Consult Medical Monitor if continuation is in patient's best interest. In addition, for QTc hospitalize patient and perform cardiology evaluation (see Section 9.1.4.3.1)
appearance			drug	drug

# 9.1.3.1. Requirements for Continuation of Treatment Post Cycle 1

Patients must fulfill the following criteria in order to commence a new cycle of treatment:

- all related  $\geq$  Grade 3 AEs have resolved to  $\leq$  Grade 1
- serum potassium and magnesium above the lower limit of normal
- no arrhythmias, pathologic bradycardia, or associated symptomology
- $QTcF \le 470$  msec and increase from baseline  $\le 60$  msec unless Medical Monitor has given permission to continue
- no concurrent medications that prolong QTc (see Appendix 4)
- no evidence of progressive disease
- no additional therapeutic interventions for glioblastoma
- no strong inhibitors or inducers of CYP3A4, CYP2C8, CYP2D6 or CYP1A2 (see Appendix 4)

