## 3.10.2 Clinical Laboratory Evaluation

The summary statistics (including number, mean, standard deviation, median, minimum and maximum) of all laboratory variables and changes from baseline will be calculated for each visit or study assessment by treatment group. For parameters of white blood cell counts, neutrophils (absolute count), lymphocytes (absolute count), monocytes (absolute count), hemoglobin, platelets, ALP, ALT, aspartate aminotransaminase, gamma glutamyl transferase, total bilirubin, glomerular filtration rate, plots of mean/mean changes from baseline with the corresponding standard error will be displayed.

For shift tables, laboratory results will be classified using the CTCAE Version 4.03. All graded laboratory parameters will be summarized separately for hematology and biochemistry. Corresponding shift tables comparing baseline to the worst post-baseline grade within the treatment period will be provided.

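### Protocol 11.3.9 leaves the Grade 3 sodium exception in 9.1.3 and the synopsis without content, and the table-grading rules in SAP 3.10 and protocol 13.4.6.5 omit the modified sodium and creatinine grading

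*Protocol*

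**What the plan says.** **Grading.** Protocol 11.1 makes CTCAE the default and leaves room for study-specific rules: "Version 4.03 will be used for grading toxicities unless otherwise specified". Section 11.3.9 uses that room twice. For sodium, "values of 126–130 mmol/L will be considered to be Grade 2 and values of 120–125 mmol/L will be considered Grade 3". For creatinine, the grade is set relative to the ULN and not relative to the patient's own baseline. The Safety assessments entry of the synopsis also names CTCAE 4.03, but without the qualifier in 11.1 and without either modification.

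**Dose modification.** Drug-related events of Grade 3 or higher lead to interruption, apart from a short list of exceptions. One exception, in the synopsis and again in 9.1.3, is "Grade 3 sodium values $\geq$ 126 mmol/L in a patient with diarrhea". The dose-adjustment table in 9.1.3 gives "No action with study drug" for Grade 2 and "Interrupt treatment until resolved to Grade 0-1" for Grade 3. It has no sodium entry. Neither 9.1.3 nor its table refers to 11.3.9.

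**Tables.** SAP 3.10.2 says that for shift tables "laboratory results will be classified using the CTCAE Version 4.03". SAP 3.10.1 grades adverse events on the same version of CTCAE. Protocol 13.4.6.5 classifies laboratory results by CTCAE 4.03 and calls for displays of Grade 3 or higher abnormalities and of grade shifts. None of the three mentions the sodium or creatinine modification.

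**The concern.** An exception written for Grade 3 sodium at or above 126 mmol/L makes sense only if such values can be Grade 3. Section 11.3.9 says they cannot. The two places therefore seem to have been written against different sodium scales, and the text does not tell a site that reads only one of them that the other exists.

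In the dose-adjustment table, Grade 2 and Grade 3 lead to different handling: no action in one case, and interruption in the other, followed by restart at the reduced dose, with only one reduction allowed. A mistaken grade would therefore carry over into treatment.

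The second issue is in reporting. If sites grade by 11.3.9 and the programmer grades by unmodified CTCAE, site-assigned grades and tabulated grades can disagree for the same value. Creatinine is the more prominent of the two analytes. Section 9.1.4 lists its elevation as an adverse event of special interest, and Section 5.2 reports elevations up to Grade 3 in the existing program.

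**Working it through.** The plan states no figure on this point, so there is none to reproduce. The check is on grading limits.

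**Inputs**
- Sodium bands: 126–130 mmol/L is Grade 2 and 120–125 mmol/L is Grade 3 (protocol 11.3.9).
- Exception: Grade 3, and at least 126 mmol/L, and diarrhea (synopsis, Study design; 9.1.3).
- Actions for a related event at first appearance: none at Grade 2, interruption at Grade 3 (dose-adjustment table in 9.1.3).
- Precedence: CTCAE 4.03 unless the protocol specifies otherwise (11.1).

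**Step 1: what the exception covers.** The values covered are those that are Grade 3 and also at least 126. Under 11.3.9 Grade 3 is 120 to 125, and no value in that band reaches 126. Listing every value from 119 to 131 mmol/L, in steps of 1 and again in steps of 0.1, gives no value that meets both conditions. The exception is empty with or without diarrhea.

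**Step 2: what action follows on each reading.** The last two columns take 9.1.3 alone and count the value as Grade 3, as the wording of the exception presupposes.

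| Sodium (mmol/L) | 11.3.9 applied, any patient | 9.1.3 alone, with diarrhea | 9.1.3 alone, without diarrhea |
|---|---|---|---|
| 120–125 | Grade 3: interrupt | interrupt | interrupt |
| 126–130 | Grade 2: no action | no interruption | interrupt |

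The readings agree everywhere except in one cell: 126–130 mmol/L in a patient without diarrhea.

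**Step 3: the boundary.** On the 0.1 grid, the nine values from 125.1 to 125.9 fall in neither band of 11.3.9. The whole-number grid has no such gap between 120 and 130. The documents do not say to what precision sodium is reported, so whether this gap matters in practice is unknown.

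**Step 4: the table rules beside the grading rules.**

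| Item | Protocol 11.3.9 | SAP 3.10.1, 3.10.2 and protocol 13.4.6.5 |
|---|---|---|
| Sodium | study-specific bands | CTCAE 4.03, no modification mentioned |
| Creatinine | against the ULN, not baseline | CTCAE 4.03, no modification mentioned |

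SAP 3.1.2, on changes from the protocol, is generic and lists no change to laboratory grading. The CTCAE sodium and creatinine limits themselves are not in the documents. How many table entries would move between grades therefore cannot be calculated.

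**The case against.** A reader might infer from the empty exception that the protocol orders opposite actions for the same sodium value. The documents do not support that, for three reasons.

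- **Precedence is stated.** Section 11.1 gives way to study-specific grading, and 11.3.9 is study-specific grading. Values of 126–130 are then Grade 2 for every patient, and the table gives one action: none.
- **The patients the exception names are unaffected.** With diarrhea, both readings lead to no interruption.
- **The conflicting cell is an inference.** Section 9.1.3 assigns no sodium grades. That values of 126 or more without diarrhea are Grade 3 is implied by the wording and stated nowhere. Interruption also needs an event that the investigator considers drug-related, and under 11.3.9 a laboratory abnormality is recorded as an adverse event only if judged clinically significant. A sodium value alone does not trigger interruption.

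All of this stands, and it reduces the dosing issue to a risk of inconsistent application. It does not remove the point. Precedence settles the grade only by leaving the exception in two places with nothing to do. A site working from the synopsis also sees the exception and an unqualified reference to CTCAE, but not the sodium bands.

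On the SAP, it is fair to say that it follows the protocol's own statistical section, which is equally silent, and that SAP Section 1 describes its procedures as those the protocol specifies. A reader might infer that the SAP overrides or disregards the protocol's grading. The text shows only an omission shared by both documents. That widens the correction to 13.4.6.5; it does not make it unnecessary.

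**Conclusion.** The point holds as an internal inconsistency of minor severity, in two parts.

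1. **Sodium.** Under 11.3.9 the exception in 9.1.3 and the synopsis covers no value. The exposure is limited to a drug-related event with sodium of 126–130 mmol/L, in a patient without diarrhea, at a site that grades from the synopsis or 9.1.3 without 11.3.9. For such a patient the difference is between no action and an interruption that uses the one permitted dose reduction. Values between 125 and 126 have no stated grade.
2. **Tables.** Followed literally, SAP 3.10.1 and 3.10.2 and protocol 13.4.6.5 drop the protocol's sodium bands and its creatinine rule. A reader might conclude that the Grade 3 tables will be wrong. The documents support only that they may not match the protocol's grading.

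The number of patients or entries affected cannot be computed for either part. The verdict assumes that 11.1 gives 11.3.9 precedence over CTCAE, which is the natural reading, and that no separate programming document already carries the modifications. SAP Section 4 leaves the list of tables to a separate document that is not available here.

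**What to change.** - **Protocol.** The synopsis (Study design and Safety assessments), 9.1.3 and 11.3.9 must be reconciled on sodium, including values between 125 and 126 mmol/L. Which limit or management rule is right is for the sponsor's clinical team, and this review takes no position on it. A cross-reference from 9.1.3 and its dose-adjustment table to 11.3.9 would stop the sections being read apart.
- **SAP 3.10.1 and 3.10.2, and protocol 13.4.6.5.** State that adverse-event and laboratory grading uses CTCAE 4.03 as modified by protocol 11.3.9, as reconciled, for sodium and creatinine.

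The cost is one protocol clarification and about one sentence in each statistical section. No new data, visits or analyses are needed.
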